### **Evaluation of Safety**

The safety and tolerability of corticosteroid administration will be evaluated by means of recording serious adverse events in both groups (frequency and type of SAEs). The DSMB will review all serious adverse events.

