	
Inclusion Criteria
 
 
1. Are admitted to an ICU
 
2. Have already received a short course (defined below) of corticosteroid specifically for acute respiratory failure, this will include patients:             
 
a. randomized to corticosteroid arm in Early Cohort and completed 10 days of corticosteroid as per Early Cohort protocol
 
b. patients with COVID who have received between 8-12 days of corticosteroids as standard of care
 
c. others who have received between 8-12 days of corticosteroids for AHRF
 
 
 
 
OF NOTE: the initial corticosteroid does not have to be dexamethasone and corticosteroids can be at any initial dose
 
 
3. Ongoing AHRF requiring HFNC, NIV (continuous positive airway pressure [CPAP] or bilevel) or invasive ventilation
 
 
Exclusion Criteria
 
 
1. An alternate indication for ongoing corticosteroids
 
2. Acute traumatic brain injury this hospital admission.
 

Study Assessments:	Study assessments are depicted in the Study Schema section.
Safety Variables & Analysis:	The safety and tolerability of corticosteroid administration will be evaluated by recording frequency and type of serious adverse events in both groups.
Statistical Analysis:	All analyses, interim and final, will use the intention-to-treat principle. The baseline characteristics comparing randomized groups will be reported using means (and standard deviations), medians (and interquartile ranges) or proportions. Trial data will be analyzed using Bayesian hierarchical generalized linear models to estimate the posterior probability of superiority (or inferiority) and equivalence for each intervention within each cohort. Additional details on statistical analysis are included in section Analyses and the PRACTICAL Master Statistical Analysis Plan (SAP).

[figure not shown]

---

---

[figure not shown]

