#### Secondary Outcomes

1. Mortality at other endpoints (ICU/hospital discharge, 30 days and 6 months)
2. Hospital length of stay
3. Duration of NIV
4. Duration of supplemental oxygen use
5. Ordinal scale of daily respiratory support\*\*
6. Need for ECLS
7. Duration of ECLS (for those that require ECLS)
8. Ventilator-free days (VFDs) censored at day 30
9. Health-related quality of life at 6 months (measured with EQ-5D)
10. *Complications from Corticosteroids:*
  - a. Hyponatremia (serum sodium > 150 mmol/L)

- b. Hyperglycemia (requiring new insulin or increase in insulin by >30% from initial/baseline dose)
- c. Delirium
- d. Clinically important GI bleeding (requiring endoscopy or RBC transfusion)
- e. Nosocomial infection
- f. Neuromuscular weakness

\*\*The daily respiratory support ordinal scale will use longitudinal proportional odds to categorize each patient's daily respiratory support needs for 30 days. Each patient will be assigned one of the following ordinal categories each day: 6 (no support), 5 (supplemental oxygen), 4 (high flow nasal cannula), 3 (non-invasive ventilation), 2 (invasive mechanical ventilation), 1 (extracorporeal life support), 0 (death). We will assess daily respiratory support needs using Markov longitudinal proportional odds modelling to estimate an odds ratio. This represents a novel scale that will be assessed compared to the other patient-important outcomes listed above.

---

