## SAFETY AND REPORTING REQUIREMENTS

Critically ill patients are admitted to the ICU for life-sustaining therapies (e.g. mechanical ventilation, vasopressors, renal replacement therapy). Many of the potential participants will be admitted with the expectation of receiving end-of-life care and possibly dying in the ICU. Furthermore, medical complications are likely to occur in this population, consistent with the nature of their severe illness (e.g., nosocomial infections; septic shock; multi-organ failure; need for vasopressors; acute renal failure and need for renal replacement therapy; arrhythmias; cardiac arrest; coma; aspiration; venous thromboembolism). Due to these relatively unique morbidity and mortality expectations in the critically ill patient population and the intervention's safety profile, generic adverse events will not be collected for this study and only studyprocedure related SAEs will be collected and reported (see section below). Expected events occurring in the course of critical illness, and not related to the study drug, will not be reported as SAEs in the CORT-E2 trial.

[figure not shown]

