### Serious Adverse Event

A serious adverse event (SAE) in the CORT-E2 trial is defined as:

- a) any event that is fatal or immediately life threatening, permanently disabling, severely incapacitating, or requires prolonged inpatient hospitalization,
- OR...**
- b) any event that may jeopardize the patient and requires medical or surgical intervention to prevent one of the outcomes listed above,
- AND...**
- c) which the attending physician believes to be **related\*** to the study drug

*\*A related event is an event in which there is a reasonable possibility that the study procedure caused or contributed (definitely, probably, or possibly) to the SAE; this conclusion may be supported by the following observations, though these are not required for the determination of relatedness:*

- *There is a plausible time sequence between study drug administration and onset of the SAE;*
- *There is a plausible biological mechanism through which study drug may have caused or contributed to the SAE;*

---

---

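### SAE frequency cannot serve as the between-arm safety evaluation, because an event counts only if attributed to the study drug; separately, the sodium outcome's label contradicts its threshold

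*Protocol*

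**What the plan says.** **What the safety evaluation uses.** Evaluation of Safety (under Statistical Analyses) relies on "recording serious adverse events in both groups (frequency and type of SAEs") and has the DSMB review all SAEs. The synopsis gives the same basis: "recording frequency and type of serious adverse events in both groups". Neither place mentions the corticosteroid complications listed as secondary outcome 10.

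**What counts as an SAE.** The Serious Adverse Event section requires seriousness (limb a or b) and also limb c, an event "which the attending physician believes to be" related to the study drug. The opening of Safety and Reporting Requirements says that generic adverse events are not collected, that "only studyprocedure related SAEs will be collected and reported", and that expected events of critical illness "not related to the study drug, will not be reported as SAEs".

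**How relatedness is worded.** Limb c refers to the study drug. The note explaining it asks for a "reasonable possibility that the study procedure caused or contributed" to the event.

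**The sodium complication.** Item 10a reads "Hyponatremia (serum sodium > 150 mmol/L") in the Secondary Outcomes section, and the synopsis has the same pairing.

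**The concern.** A count of serious events by arm informs about harm only if an event has the same chance of being counted in either arm. Here the definition makes counting depend on attribution to a drug that one arm is assigned not to receive, and the person attributing knows the assignment. Any difference then mixes the drug's effect with the effect of the definition.

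Attribution is also a weak tool for the harms of interest. The safety section itself lists nosocomial infection among the complications expected in this population. For common ICU events, case-by-case judgement cannot show an excess; a count by arm regardless of attribution can.

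At stake is what the DSMB sees. An imbalance in SAEs could look like harm when there is none, and a small number could look reassuring because events were judged to be part of critical illness.

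The sodium item raises a different risk: someone following the label and someone following the threshold would record opposite abnormalities.

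**Working it through.** The protocol gives no SAE rate and no safety power, so there is no figure to reproduce. The stated 94% power concerns 60-day mortality. The point rests on setting the definitions beside the arms.

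**1. Who can have an SAE under limb c**

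| Arm | Exposure to study dexamethasone (Trial Interventions; Eligibility; Compliance) | Can limb c be met? |
|---|---|---|
| Early, intervention | Up to 10 days | Yes, if the physician attributes the event |
| Early, control | None by assignment; open-label use is captured and expected to be small | Essentially no, apart from crossovers |
| Extended, intervention | Yes | Yes, if attributed |
| Extended, control | Some patients come from the Early intervention arm with 10 days just completed; the others had 8-12 days of corticosteroid outside the Early Cohort; all then stop without a taper | Possibly, depending on earlier exposure and attribution |

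Reporting runs from randomization to ICU discharge or 30 days, whichever is shorter. An event soon after the second randomization can therefore be attributed to dexamethasone given before it. The section on minimizing bias confirms that patients and providers are unblinded.

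**2. Illustration for the Early Cohort (rates assumed)**

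A maximum of about 2000 per cohort at 1:1 gives about 1000 per arm. With 0 SAEs among 1000 controls, the smallest treated-arm count with a two-sided Fisher p below 0.05 is 6. Suppose the drug has no effect on serious events. The treated-arm count is then X ~ Binomial(1000, b × a), where b is the background rate of serious events and a is the share called at least possibly related. The last column is P(X ≥ 6).

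| b | a | Expected SAEs, treated vs control | P(nominal p < 0.05) |
|---|---|---|---|
| 10% | 2% | 1000 × 0.10 × 0.02 = 2 vs 0 | 2% |
| 10% | 5% | 5 vs 0 | 38% |
| 10% | 10% | 10 vs 0 | 93% |
| 30% | 2% | 6 vs 0 | 56% |
| 30% | 5% | 15 vs 0 | 99.7% |

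The size depends heavily on the assumptions; the direction does not. The protocol plans no such test on SAEs, so the p-value is only a yardstick for how striking the artefact would look.

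**3. Illustration when some controls are exposed (rates assumed)**

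Expected control SAEs = 1000 × exposed share × attributed SAE rate among the exposed.

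- Low end: 1000 × 0.05 × 0.005 = 0.25.
- High end: 1000 × 0.30 × 0.03 = 9.

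The count is low but not zero by definition, and it is driven by exposure and attribution.

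**4. What is still comparable (rates assumed)**

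Outcomes 10a-f carry no relatedness condition. Take nosocomial infection (10e) at 20% against 25% with 1000 per arm, that is 200 against 250 events:

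- SE = √(0.20 × 0.80/1000 + 0.25 × 0.75/1000) = 0.0186
- z = 0.05/0.0186 ≈ 2.68 (with the unrounded SE)

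The present protocol would already record this contrast by arm. It is simply not named as the safety evaluation.

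**5. Sodium**

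Hyponatremia means low sodium; a value above 150 mmol/L is high sodium (hypernatremia). The contradiction stands in both the synopsis and the outcome list. The Study Assessment Schema has sodium reported at baseline and daily (daily data run for the ICU stay, up to day 30), so the values needed under a consistent definition are being collected.

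**The case against.** The strongest reply is that limiting SAEs to related events is a declared choice, with reasons given: serious events are expected in this population and generic reporting would add noise. The protocol announces no test on SAEs and no SAE stopping rule. The triggers concern mortality only, including one for inferiority. Complications are prespecified separately, and subjective ones such as nosocomial infection go to a blinded adjudication committee. Detail on tabulation may sit in the Master Protocol or the SAP. All of this is fair. It narrows the point to what SAE counts can support, but it does not repair the two places that rest the safety evaluation on those counts in both groups. An SAP cannot recover as SAEs the events that sites are told not to report as such.

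Two stronger readings are tempting. A reader might infer that control SAEs are zero by construction throughout the trial. The documents do not support that: Extended controls may have just finished study dexamethasone, crossovers are anticipated, and the wording about study procedure could admit events linked to the assigned stopping of treatment. A reader might also infer that the trial can neither detect nor exclude harm. That fails too, because outcomes 10a-f and mortality are compared by arm without attribution.

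On sodium, the objection that the threshold is explicit and the error can be corrected from collected values is right. It makes the point small, not void.

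**Conclusion.** The point holds as a contradiction between the safety evaluation and the SAE definition. In the Early Cohort the control count is essentially zero apart from crossovers, so the arm contrast is largely produced by the definition. In the Extended Cohort the control count can be above zero but is governed by prior exposure and unblinded attribution. In neither cohort can SAE frequency be interpreted as a between-arm comparison of safety.

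The conclusion rests on the protocol's definitions and needs no assumed rate. The illustrative sizes (2 to 15 against 0 in the Early Cohort with no true effect; 0.25 to 9 control SAEs per 1000 where 5-30% of controls are exposed) rest entirely on assumed rates.

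The mismatch between study drug and study procedure is part of the same problem, because it leaves open which control events qualify. The sodium contradiction is certain, separate and minor.

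**What to change.** 1. **Synopsis (Safety Variables & Analysis) and Evaluation of Safety.** State that the between-arm safety comparison uses outcomes 10a-f, recorded in all patients in both arms regardless of attribution and reported by arm to the DSMB.
2. **Same places.** State that attributed SAEs are listed descriptively in whichever arm they occur and are not used as a between-arm comparison. The listing should not be confined to the intervention arms: that would drop attributable SAEs in Extended controls, which the section on reporting and follow-up requires to be reported.
3. **Safety and Reporting Requirements, and Serious Adverse Event.** Reconcile study drug with study procedure, so that sites know which events qualify, particularly in the Extended control arm.
4. **Outcome 10a.** Make label and threshold agree in the synopsis and in Secondary Outcomes, and check that the case report form matches.

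The cost is essentially wording. Outcomes 10a-f are already secondary outcomes and sodium is already collected daily. The only operational step is to ensure that the DSMB reports show 10a-f by arm.

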### **Analyses**

Any deviation from the original statistical plan will be described in the final report.

[figure not shown]

All analyses, interim and final, will use the intention-to-treat principle. The baseline characteristics comparing randomized groups will be reported using means (and standard deviations), medians (and interquartile ranges) or proportions. Trial data will be analyzed using Bayesian hierarchical generalized linear models to estimate the posterior probability of superiority (or inferiority) and equivalence for each intervention within each domain. The hierarchical model will account for centre, time period, sex and oxygen support at the time of randomization (HNFC, NIV, invasive mechanical ventilation or ECLS). Posterior probability distributions will be computed by combining the likelihood function with minimally informative priors and updated every three months as information (observations) accumulate in the trial. Statistical analysis will be adjusted for whether a patient was enrolled in one CORT-E cohort or both CORT-E cohorts. We do not expect interaction between CORT-E and the other PRACTICAL domains. The final study analysis, separate for each cohort, will be completed once either superiority, inferiority or equivalence has been observed and confirmed by the DSMB and Platform Steering Committee.

We will collect sex and perform subgroup analysis based on this variable. It is less feasible to collect gender as most patients will not be conscious at the time of enrolment. We don't expect effect modification for either cohort based on sex or gender. Understanding the CORT-E eligibility criteria, we plan to enroll a diverse population of patients representative of the demographics of ICU patients presenting at the participating sites.

As above, in keeping with the Bayesian framework, frequent reassessments of posterior distribution will occur. We plan to perform these analyses after each 200 patients have been randomized (after we have primary outcome data for each 200 patients). We will not start these interim analyses until at least 750 patients have been enrolled (again, until we have outcome data for at least 750 patients) in each domain in order to decrease the likelihood of spurious early findings based on an insufficient number of observations. These analyses will remain blinded to all study investigators and will be reviewed only by the DSMB. If stopping criteria are met, the DSMB may suggest stopping enrolment to one or both cohorts. The stopping criteria are intentionally conservative to avoid inappropriately stopping the trial early.

Six subgroups apply to both cohorts: 1) patients < 65 versus  $\geq$  65 years (hypothesizing that younger patients will benefit more from early and extended corticosteroids); 2) patients requiring HFNC or NIV versus invasive mechanical ventilation at the time of randomization (hypothesizing that patients receiving invasive ventilation will benefit more from early and extended corticosteroids); 3) male vs. female sex (hypothesizing no difference); 4) those requiring ECLS at baseline versus not requiring ECLS (hypothesizing that those requiring ECLS will benefit more

from early and extended corticosteroids; and 5) patients requiring versus not requiring vasopressor support at randomization (hypothesizing that those requiring vasopressor support will benefit more from early and extended corticosteroids). Two subgroups will apply exclusively to Extended Cohort 1) patients with COVID versus those with non-COVID AHRF (hypothesizing that those with COVID will benefit more from extended corticosteroids), 2) patients enrolled only in Extended Cohort versus those enrolled in both Early Cohort and Extended Cohort (to assess for interaction between cohorts). We will collect plasma samples at baseline to allow for post-hoc subgroup analysis for Early Cohort and Extended Cohort based on inflammatory groups (hypothesizing that those with elevated inflammatory markers [IL-6, sTNFr1 and IL-8] will benefit more from corticosteroids). We will perform these subgroup analyses only for the primary outcome.

[figure not shown]

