##### **Extended Cohort**

##### Inclusion Criteria

1. Are admitted to an ICU
2. Have already received a short course (defined below) of corticosteroid specifically for acute respiratory failure, this will include patients:

- a. randomized to corticosteroid arm in Early Cohort and completed 10 days of corticosteroid as per Early Cohort protocol
  - b. patients with COVID who have received between 8-12 days of corticosteroids as standard of care
  - c. others who have received between 8-12 days of corticosteroids for AHRF
- OF NOTE: the initial corticosteroid does not have to be dexamethasone and corticosteroids can be at any initial dose
3. Ongoing AHRF requiring HFNC, NIV (continuous positive airway pressure [CPAP] or bilevel) or invasive ventilation

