### **Patient Randomization**

General registration information can be found in the PRACTICAL Master Protocol.

[figure not shown]
Prior to randomizing a patient, each institution must have submitted all necessary regulatory documentation to Ozmosis Research Inc. and received a local activation letter. Access to the eCRFs will be granted once this has been received and randomization will occur online via the REDCap database.

Patient eligibility must be confirmed by the principal investigator or one of the sub-investigators at the site prior to randomization into either cohort in this domain. An explanation of the study, discussion of the expected side effects, and full disclosure of the “informed consent” document must take place. Eligible and consented patients will be randomized into individual cohorts within the domain.

**Early Cohort Screening:** Patients will be screened for eligibility at the time of ICU admission. After-hours screening should be performed where possible, however the 72-hour window for enrolment in the Early Cohort should allow most patients to be captured with weekday screening alone. Patients who do not meet oxygen support thresholds for Cohort #1 at initial screening will be followed to determine if they deteriorate and meet criteria within the 72-hour post-ICU admission window.

**Extended Cohort Screening:** Patients receiving corticosteroids for any type of AHRF in the ICU should be tracked (including patients that are receiving treatment as part of the Early Cohort). Patients that were included in the Early Cohort that remain on treatment for 10 days should be screened for eligibility for a second randomization into the Extended Cohort, and randomized on day 10 of treatment, if eligible. Patients that are receiving their initial course of corticosteroid as part of SOC (and not as part of the Early Cohort), can be screened and if they meet Extended Cohort eligibility criteria after 8-12 days of corticosteroid treatment, they can be approached for consent and possible randomization into the Extended Cohort.

For patients who are receiving their initial course of corticosteroids as part of standard of care and are eligible for the Extended Cohort, randomization into the Extended Cohort should be prioritized at 10 days, or as close to 10 days as possible. However, randomization into the Extended Cohort two days shorter or two days longer are acceptable depending on the initial

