## TRIAL INTERVENTIONS

### Early Cohort

#### Intervention Arm:

[figure not shown]
Patients randomized to receive corticosteroids will receive dexamethasone 20mg daily for 5 days and then 10mg for an additional 5 days, for a total of 10 days or until ICU discharge or death, whichever comes first. After 10 days dexamethasone will be stopped without a taper. If a patient is discharged from the ICU prior to completing the protocol, then ongoing corticosteroid management will be up to the treating team as per SOC.

Dexamethasone will be administered parenterally (intravenous administration). Specific details on the timing of administration are provided below;

- 20mg dexamethasone is to be administered as soon as possible and on the day of randomization (Day 0), and this dose will be administered daily for a total of 5 days of treatment (Day 0 – Day 4). Then, the dexamethasone dose will be reduced to 10mg and this dose will be administered daily for a total of 5 days (Day 5 – Day 9).
- In rare cases where it is not possible to administer the first dose of study drug on the same day as randomization (e.g., if the patient is randomized very close to midnight), 20 mg dexamethasone can be started the day following randomization (Day 1), and will be administered daily for a total of 5 days of treatment (Day 1 – Day 5). Then, the dexamethasone dose will be reduced to 10mg and this dose will be administered daily for a total of 5 days (Day 6 – Day 10).

Patients finishing 10 days of dexamethasone as part of the Early Cohort will be eligible for randomization in the Extended Cohort if they are still requiring HFNC, NIV, IMV or ECLS, and according to the other eligibility criteria for the Extended Cohort.

**Control Arm:** Those randomized to usual care will receive routine AHRF management without corticosteroids. All other aspects of care will be at the discretion of the treating team including antibiotics, intravenous fluids, mechanical ventilation and ECLS.

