### **MINIMIZING SOURCES OF BIAS**

The online randomization system will ensure allocation concealment and employ variable block sizes. Patients and treating healthcare providers will not be blinded. While blinding is an important mechanism to mitigate performance and detection bias, blinding would not allow for subsequent randomization of those that receive dexamethasone in the Early Cohort to further randomization in the Extended Cohort, thereby eliminating our efficiency and ability to answer multiple questions within the same trial. We will mitigate outcome ascertainment bias by using relatively objective outcomes not easily influenced by knowledge of treatment assignment (e.g. mortality). We will blind data analysts and statisticians. For the few subjective outcomes (e.g., nosocomial infections), we will establish a blinded adjudication committee that will evaluate events using standardized and accepted definitions to limit risk of bias.

We will collect data related to co-interventions to evaluate whether lack of blinding leads to differential use of specific interventions or treatments and will provide protocols for ventilation, and supportive therapy best practices to help ensure consistency. We will also minimize bias by using an intention-to-treat analysis and minimizing loss to follow-up. Missing data will also be minimized through use of a clear and comprehensive data dictionary with online data entry using logical consistency rules.

---

---

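### The adjustment for enrolment in one or both cohorts is not limited to the Extended Cohort; applied as written to the Early Cohort model, it conditions on a post-randomisation event almost confined to the steroid arm

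*Protocol*

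**What the plan says.** The Analyses section lists the terms of the hierarchical model as centre, time period, sex and oxygen support. It then adds: "Statistical analysis will be adjusted for whether a patient was enrolled in one" of the two cohorts or both. No cohort is named. The same section states: "All analyses, interim and final, will use the intention-to-treat principle". It also says: "The final study analysis, separate for each cohort, will be completed once either superiority, inferiority or equivalence has been observed". The Sample Size section evaluates the three stopping triggers separately in each cohort.

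The route from one cohort to the other is set elsewhere:

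- Extended Cohort inclusion criterion 2a covers patients "randomized to corticosteroid arm in Early Cohort and completed 10 days of corticosteroid as per Early Cohort protocol".
- Criterion 3 requires "Ongoing AHRF requiring HFNC, NIV (continuous positive airway pressure [CPAP] or bilevel) or invasive ventilation", and criterion 1 requires the patient to be in an ICU.
- Under Patient Randomization, Early Cohort patients still on treatment at 10 days "should be screened for eligibility for a second randomization into the Extended Cohort, and randomized on day 10 of treatment, if eligible".
- For Early Cohort controls, Trial Interventions says: "Those randomized to usual care will receive routine AHRF management without corticosteroids".
- Criterion 2c also admits other patients who have had 8 to 12 days of corticosteroids for AHRF. The section on compliance and dropout expects few crossovers.

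**The concern.** The same indicator means different things in the two cohorts. At Extended Cohort randomisation, earlier membership of the Early Cohort is already known and cannot be affected by the Extended assignment, so adjusting for it is proper.

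At Early Cohort randomisation, membership of both cohorts lies in the future. To acquire it a patient must, in practice, be assigned to dexamethasone, survive to about day 10, complete the course, remain in ICU on support, and consent again. The indicator is thus a consequence of assignment and of prognosis. A model that holds it fixed does not estimate the effect of assignment in everyone randomised, which is what the intention-to-treat statement promises.

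At stake is the Early Cohort primary estimate and every interim decision based on it, in a cohort of up to about 2000 patients.

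**Working it through.** **1. What the coefficient estimates.** Let T = 1 for the steroid arm and B = 1 for enrolment in both cohorts. If B = 1 occurs only when T = 1, the model logit(p) = a + bT + cB has three parameters for three groups and fits them exactly:

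b = logit(risk | T = 1, B = 0) − logit(risk | T = 0)

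So b compares steroid patients who were not re-randomised with all controls. If M is the mortality of the whole steroid arm, q the share re-randomised and m their mortality, the risk in the T = 1, B = 0 group is

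r = (M − q·m) / (1 − q)

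The other model terms do not change this logic. The identity is exact only for the two-term model.

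**2. Inputs.** The protocol gives neither q nor m. It gives no control risk for its simulations, only a background mortality range of 20% to 50%. I assume no true effect and M = 34% in both arms, so the control odds are 0.34/0.66 = 0.515.

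**3. Adjusted odds ratio when the true odds ratio is 1.0.**

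| q | m | r | odds of r | adjusted OR |
|---|---|---|---|---|
| 10% | 40% | (0.34 − 0.040)/0.90 = 0.333 | 0.500 | 0.97 |
| 10% | 30% | (0.34 − 0.030)/0.90 = 0.344 | 0.525 | 1.02 |
| 20% | 37% | (0.34 − 0.074)/0.80 = 0.333 | 0.498 | 0.97 |
| 20% | 45% | (0.34 − 0.090)/0.80 = 0.313 | 0.455 | 0.88 |
| 30% | 45% | (0.34 − 0.135)/0.70 = 0.293 | 0.414 | 0.80 |
| 20% | 25% | (0.34 − 0.050)/0.80 = 0.363 | 0.569 | 1.10 |
| 30% | 25% | (0.34 − 0.075)/0.70 = 0.379 | 0.609 | 1.18 |

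The bias is zero only when m = M, that is, when re-randomised patients have the same mortality as the rest of their arm.

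**4. Effect on the triggers.** I simulated 20,000 trials per row, with looks at 750 patients, then every 200, then at 2000. The rules were the stated ones: 99% for superiority, 99% for inferiority and 90% for equivalence, with a flat-prior normal approximation.

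The plan's own figure comes first. The Sample Size section states a type I error below 5%. Without the indicator, false superiority and false inferiority are each about 3%, consistent with that statement.

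With the indicator:

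| q | m | false superiority | false inferiority |
|---|---|---|---|
| 10% | 40% | about 5% | – |
| 10% | 30% | – | about 5% |
| 20% | 37% | about 6% | – |
| 20% | 45% | about 21% | – |
| 30% | 45% | about 49% | – |
| 20% | 25% | – | about 16% |
| 30% | 25% | – | about 34% |

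**5. Controls who enter through criterion 2c.** Take a control risk of 35%, 20% of the steroid arm re-randomised, 50% mortality among entrants and no true effect. The adjusted odds ratio is 0.845, 0.862 and 0.885 when 0.1%, 2% and 5% of controls enter. Control entry shrinks the bias but does not remove it.

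**6. Direction.** A separate null simulation gave each patient an underlying frailty. The odds ratio without the term stayed at 0.995 to 1.009. With the term it was 0.74 to 0.98 where entrants were sicker than the rest of the arm, and 1.02 to 1.07 where most deaths fell before day 10. Either sign is possible.

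**The case against.** **The protocol never says that the Early Cohort model carries this term.** A reader might infer from the sentence that it is planned there and that the primary estimate is therefore biased. The text does not go that far. The sentence names no cohort, the indicator is absent from the preceding list of model terms, and intention to treat is stated. The matching subgroup (Extended only versus both) is limited to the Extended Cohort, which suggests that the authors may have meant only the legitimate use. The master SAP, not shown here, may say so. What remains is that the authors did write the limit for the subgroup and not for the adjustment, while the analyses are separate for each cohort. A statistician who follows the sentence literally would fit the term in both models.

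**The size is assumed.** This stands. A reader might infer that type I error control is necessarily lost, or that the error favours dexamethasone. Neither follows. With 10% re-randomised and modest differences in mortality, the error rates stay near the 5% bound, and the sign depends on who is re-randomised.

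**Controls can enter.** This is true through criterion 2c. It weakens the bias but, as shown, does not remove it.

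**Blinding.** The protocol says "We will blind data analysts and statisticians", and a reader might infer that the covariate would reveal the arm. That is not a consequence of the adjustment. Re-randomisation is in the trial data whether or not it is modelled, and the Extended Cohort subgroup needs the linkage anyway.

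**Conclusion.** The sentence is wrong as written because it is unrestricted. Applied to the Early Cohort, it conditions on an event that follows randomisation, depends on prognosis and is almost confined to one arm. The resulting coefficient is not the intention-to-treat contrast. The algebra is firm. That this model is what the authors intend is not established.

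Under no true effect and 34% mortality, the consequence runs from negligible (odds ratio 0.97 or 1.02, error about 5%) to severe (0.80 with about 49% false superiority, or 1.18 with about 34% false inferiority). The comparator is about 3% for each error without the term. These figures rest on assumed values for the share re-randomised and their mortality, and on no control entry. The Extended Cohort analysis is unaffected.

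**What to change.** In the Analyses section, replace the sentence with:

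*In the Extended Cohort model only, the analysis will be adjusted for prior enrolment in the Early Cohort. The Early Cohort model will include no term for later enrolment in the Extended Cohort.*

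The master SAP should carry the same restriction. The cost is two sentences. No data, patients or further analyses are needed.
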